12.4.5 Collection and Recording of Adverse Events and Serious Adverse Events

The Investigator or site staff is responsible for detecting, documenting, and reporting events that meet the definition of an AE or SAE.

Adverse events will be collected from the time of signing the ICF until the last contact.

Serious adverse events will be collected over the same time period as stated above for AEs. However, any SAEs assessed as related to study participation (e.g., IP, protocol mandated procedures, invasive tests, or change in existing therapy) or related to a concomitant medication that is a Sponsor product will be recorded from the time a subject consents to participate in the

study up to and including any follow-up contact. All SAEs will be reported to the Sponsor within 24 hours, as indicated in [Section 12.4.2](#).

The Investigator will enquire about the occurrence of AEs/SAEs at every visit throughout the study (including Follow-up and Discontinuation visits where applicable) by asking the following non-leading verbal question of the subject (or care-giver, where appropriate):

- “Have you had any medical problems since your last visit?”

All AEs not resolved by the end of the study or that have not resolved upon the subject’s discontinuation in the study must be followed until the event resolves, the event stabilizes, or the event returns to baseline if a baseline value is available.

All AEs regardless of seriousness, severity, or relationship to the study medication must be recorded on the AE pages of the CRFs/eCRFs.

Adverse events that meet the definition of a SAE must be reported on the SAE Form provided for this study.

Adverse events must be documented in clear, unambiguous medical language. Do not use abbreviations or acronyms.

For each AE, record only the diagnosis; do not report the characteristic signs and symptoms of the diagnosis as additional AEs.

If a diagnosis is unavailable, each sign and symptom should be recorded as an AE. Update the AE CRF/eCRF record with the relevant diagnosis alone, when this is available.

In general, abnormal findings at screening should be recorded in the subject’s Medical History or in the Concurrent Conditions section in the CRF/eCRF. However if, in the Investigator’s opinion, the finding is clinically significant and represents a condition that was not present at the signing of informed consent, then the finding must be reported as an AE.

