13.7.2 Adverse Events

Adverse events will be coded using the current Medical Dictionary for Regulatory Activities (MedDRA). Adverse events occurring between the signing of informed consent and administration of the first dose of randomized study medication will be regarded as pre-treatment AEs and included in the subject listings but not in the summary tables. Adverse events occurring after the first dose of randomized study medication will be defined as TEAEs.

The safety endpoints related to AEs are:

- Proportion of subjects with TEAEs.
- Proportion of subjects with treatment-related TEAEs.
- Incidence, type, and severity of the TEAEs after 30 weeks of study treatment.
- Incidence, type, and severity of the TEAEs after 52 weeks of study treatment.

The number and percentage of subjects with TEAEs will be summarized by study treatment group, overall, and by system organ class (SOC) and preferred term (PT) using frequency counts and percentages. The summaries will also include the number of TEAEs experienced. A similar summary will be produced for subjects with treatment-related TEAE.

The number and percentage of subjects with a TEAE that has a start date within 30 weeks of the start of treatment (≤ 182 days) will be summarized by severity and study treatment group, overall, and by SOC and PT using frequency counts and percentages. A similar summary will be produced including all TEAEs during the study (i.e., after 52 weeks of treatment).

If sufficient data exist, TEAE frequencies will be compared across treatment groups using Fisher's exact test or a similar test.

Additionally, the number and percentage of SAEs, TEAEs leading to discontinuation, and TEAEs related to the IP will be summarized by SOC, PT, and study treatment group. All AEs will be displayed in listings. AEs that occur during the run-in period will be summarized separately.

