## 8.0 Sample Size Determination

The sample size of 600 subjects for this study (400 subjects on GSP 301 NS and 100 subjects in each of the 2 placebo groups) is based on the ICH E1 Guideline (ICH E1) and the FDA Guidance on Allergic Rhinitis which requires treatment of at least 300 subjects for 6 months and 100 subjects for 1 year. Based on an estimated attrition rate of 25% after 6 months and 50% after 52 weeks, 400 subjects in the GSP 301 NS treatment group are considered sufficient to meet the above requirements.

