### **Safety Analysis Set (SAS)**

The Safety Analysis Set (SAS) will consist of all subjects who took at least 1 dose of study medication following randomization and will be used for all safety analyses.

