### 12.2.2 Adverse Events

All AEs will be coded according to the current version of MedDRA (version 18.1 or later). Adverse events occurring between the subjects signing informed consent and administration of the first dose of the randomized study medication will be regarded as pre-treatment AEs and will be included in the subject listings but not in the summary tables. Adverse events occurring after the first dose of the randomized study medication will be defined as treatment-emergent adverse events (TEAEs) and will be listed and summarized by System Organ Class (SOC) and Preferred Term (PT).

The safety endpoints related to AEs are:

- Proportion of subjects with TEAEs.
- Proportion of subjects with treatment-related TEAEs.
- Incidence, type, and severity of the TEAEs after 30 weeks of study treatment.
- Incidence, type, and severity of the TEAEs after 52 weeks of study treatment.

Summaries of the number and percentage of subjects with TEAEs and the number of TEAEs experienced will be presented by treatment group. The number of subjects and the number of TEAEs will be presented using frequency counts and percentages, overall and by SOC and PT. The percentages will be calculated as the number of subjects with TEAEs divided by the number of subjects in the safety analysis set. Tables of the number and percentage of subjects and the number of TEAEs by intensity and by relationship to study medication will also be presented. Similar tables will be created for treatment related AEs. Events will be assigned to the study treatment administered prior to the start of the TEAE. Events that occurred during discharge and final follow-up will be assigned to the final treatment.

The number and percentage of subjects with a TEAE that has a start date within 30 weeks of the start of treatment ( $\leq 182$  days) will be summarized by severity and study treatment group, overall, and by SOC and PT using frequency counts and percentages. A similar summary will be produced including all TEAEs during the study (i.e., after 52 weeks of treatment).

The overall p-value of the comparison among three treatment groups by SOC and PT will be produced using Fisher's exact test for each SOC and PT as well as overall subjects with at least one TEAEs. .

|  |                                    |                                  |
|--|------------------------------------|----------------------------------|

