|                                |             | Events   | Subjects
n(%) | Events   | Subjects
n(%) | Events                   | Subjects
n(%) |                     |
| Subjects with at least one AEs | Total       | xxx  | xxx (xx.x)       | xxx  | xxx (xx.x)       | xxx                      | xxx (xx.x)       | x.xxxx              |
| Ear and labyrinth disorders    | Ear pain    | xxx  | xxx (xx.x)       | xxx  | xxx (xx.x)       | xxx                      | xxx (xx.x)       | x.xxxx              |
|                                | etc.        |  |                  |  |                  |                          |                  |                     |

etc.

N = Total number of subjects in each treatment group in the safety set; n = number of subjects with adverse events in each MedDRA term; Percentages are based on total number of subjects in the safety set within each treatment group.

Data source: xx

Created on: ddmmmyy hh:mm

Page 1 of N

|  |                                    |                                  |
|--|------------------------------------|----------------------------------|
| Protocol Number:
GPL/CT/2014/018/III
(Study No. GSP 301-303) | SAP Version Number:
Version 1.0 | SAP Version Date:
04-Apr-2017 |
|--|------------------------------------|----------------------------------|

**T14.1.9.5.4 Summary of Treatment Emergent Adverse Events after 30 Weeks of Study Treatment  
(Safety Analysis Set)**

Repeat of T14.1.9.5.3 for after 30 weeks of study treatment

**T14.1.9.5.5 Summary of Treatment-Related Emergent Adverse Events after 52 Weeks of Study Treatment  
(Safety Analysis Set)**

Repeat of T14.1.9.5.3 for related TEAEs after 52 weeks of study treatment

**T14.1.9.5.6 Summary of Treatment-Related Emergent Adverse Events after 30 Weeks of Study Treatment  
(Safety Analysis Set)**

Repeat of T14.1.9.5.3 for related TEAEs after 30 weeks of study treatment

**T14.1.9.5.7 Summary of Treatment Emergent Adverse Events of Special Interest  
(Safety Analysis Set)**

Repeat of T14.1.9.5.3 for AESI

**T14.1.9.5.8 Summary of Treatment Related Emergent Adverse Events of Special Interest  
(Safety Analysis Set)**

Repeat of T14.1.9.5.3 for related TEAEs of AESI

|  |                                    |                                  |
|--|------------------------------------|----------------------------------|

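### SAP 12.2.2 reports 52-week TEAE incidence as observed events over everyone dosed, which understates it under the plan's own 50% attrition

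*SAP*

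**What the plan says.** The primary objective compares safety over 52 weeks. One primary endpoint is "Incidence, type, and severity of the TEAEs after 52 weeks of study treatment" (Protocol 13.7.2, repeated in SAP 4.1).

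SAP 12.2.2 sets the percentage: "The percentages will be calculated as the number of subjects with TEAEs divided by the number of subjects in the safety analysis set". The safety analysis set "will consist of all subjects who took at least 1 dose of study medication following randomization and will be used for all safety analyses" (SAP 10.0), so length of follow-up plays no part. The numerator of the 52-week table is whatever was seen on study: "A similar summary will be produced including all TEAEs during the study (i.e., after 52 weeks of treatment". The footnote to shell T14.1.9.5.3 agrees: "Percentages are based on total number of subjects in the safety set within each treatment group". The related-TEAE and AESI shells repeat that layout, and the SAE shell uses the same denominator. SAP 12.2.2 also applies a three-group Fisher's exact test to the proportions with any TEAE and with each SOC and PT.

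On follow-up, SAP 8.0 reads "Based on an estimated attrition rate of 25% after 6 months and 50% after 52 weeks", in support of "400 subjects on GSP 301 NS and 100 subjects in each of the 2 placebo groups". Protocol 12.4.5 says "Adverse events will be collected from the time of signing the ICF until the last contact". Protocol 11.15 schedules no follow-up visit, and Protocol 9.4 rules out replacement of drop-outs.

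SAP 12.1.2.4 and T14.1.9.11.1 summarise days on treatment by arm. Neither document plans a person-time rate, a Kaplan-Meier estimate or a time-to-first-event analysis for TEAEs.

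**The concern.** A subject who leaves in Week 10 stays in the denominator for 52 weeks, but can enter the numerator only through events seen in the first 10. Ongoing events are followed after exit (Protocol 12.4.5, SAP 5.0), but new first events in people who have left are not sought. If half the subjects are expected to leave, a figure labelled as 52-week incidence describes a shorter and variable period.

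At stake is the main output of a long-term safety study. Late-onset events lose most, and the AESI list in SAP 12.2.3 includes cataract and glaucoma. Any statement that a given percentage of users had an event within a year would be too low.

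**Working it through.** **Inputs from the documents.** Attrition 25% at 6 months (taken as Week 26) and 50% at Week 52; denominator, everyone dosed; adverse event collection ends at last contact.

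**Assumed, because the documents give no values.** True 52-week risk R, the timing of first events, drop-out independent of events, and a constant drop-out hazard within each half-year.

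**1. The plan's own figure.** 300 / 0.75 = 400, and 400 × 0.50 = 200, above the 100 needed for one year. The sample size reproduces.

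**2. Follow-up.** Drop-out hazards per week:
- h1 = −ln(0.75)/26 = 0.01107
- h2 = −ln(0.50/0.75)/26 = 0.01559

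Mean follow-up = 0.25/h1 + 0.25/h2 = 22.6 + 16.0 = 38.6 weeks, and 38.6/52 = 74%.

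**3. Crude percentage, constant event hazard.** Let λ = −ln(1−R)/52 and s = √(1−R). Then

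crude = [λ/(λ+h1)](1 − 0.75s) + 0.75s · [λ/(λ+h2)](1 − ⅔s)

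For R = 10%, λ = 0.002026 and s = 0.9487:
- Weeks 0–26: 0.1548 × 0.2885 = 0.0447
- Weeks 26–52: 0.7115 × 0.1150 × 0.3675 = 0.0301
- Total 0.0747, or about 7.5%

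**4. Sensitivity to onset, at the planned attrition.** Front-loaded onset is a Weibull with shape 0.5.

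| True 52-week risk | Constant hazard | Front-loaded |
|---|---|---|
| 10% | 7.5% | 8.3% |
| 30% | 22.7% | 25.3% |
| 50% | 38.6% | 42.8% |
| 70% | 55.5% | 61.3% |

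For risks of 5–70% the crude figure is 74–79% of the true one with constant hazard and 83–88% with front-loaded onset. A 2% risk arising only after Week 26 appears as about 1.2%.

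**5. Between arms, equal drop-out.** With the planned attrition in both arms and constant hazard, a true 50% v 40% appears as 38.6% v 30.6%. Ten points become 8.0.

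**6. Between arms, unequal drop-out (hypothetical).** Take the same true 10% risk in both arms, with 40% v 60% drop-out by Week 52. A single constant drop-out hazard μ = −ln(1−d)/52 gives crude = [λ/(λ+μ)](1 − 0.9(1−d)):
- d = 40%: 0.1710 × 0.46 = 7.9%
- d = 60%: 0.1031 × 0.64 = 6.6%

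If half of each arm's drop-out falls by Week 26, the pair is 8.0% v 6.9%. The remaining results in this step use that pattern:
- True 50% in every arm, 30% drop-out on active and 60% on placebo: 43.2% v 36.2%. In 4,000 simulated trials a Fisher test of 400 v 100, at an assumed two-sided 5% level, rejects about 23% of the time. At 40% v 60% drop-out it rejects about 13%, and at the planned equal 50% about 4%.
- The reverse pattern hides harm. True 50% on active with 60% drop-out, against true 40% on placebo with 30% drop-out, shows 36.2% v 34.4%.

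**The case against.** The strongest reply is that crude n/N is the right answer to part of the question. Two of the four AE endpoints are untimed: the proportions with any TEAE and with any related TEAE. SAP 12.2.2 defines the 52-week summary operationally, as everything seen on study, and SAP 6.0 states no hypotheses. This stands: the crude tables should stay. It does not rescue the endpoint that names 52 weeks, because a reader will take that figure as one-year incidence.

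A reader might infer that every AE percentage in the plan uses the safety set. It does not. In T14.1.9.5.1 and 5.2 the severity, relatedness, death and serious rows are shares of all events reported. The point concerns the subject-level tables from T14.1.9.5.3 onward.

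A reader might also infer that drop-out will by itself produce a difference between arms. The documents give one attrition figure, used to size the active arm, and no placebo rate. Equal drop-out gives no false difference. T14.1.9.1 lists both adverse events and lack of efficacy as exit reasons, so unequal exit is possible, but it is not planned or forecast.

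The tables restricted to events by day 182 suffer less, since 182 days is 26 weeks and expected attrition there is 25%. In the 10% example the true 26-week risk is 1 − 0.9487 = 5.1% and the crude figure is 4.5%. Event counts and days on treatment are tabulated, so a rough rate could be worked out by hand. Neither gives 52-week incidence.

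Finally, time-at-risk methods carry their own assumption. If subjects leave because of intolerance or poor efficacy, censoring may be informative, and Kaplan-Meier estimates and rates can then be biased too. This stands and belongs in the SAP.

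**Conclusion.** The point holds for the subject-level 52-week tables. Provided some first events would have occurred after subjects left, the crude percentage is below 52-week incidence. The direction is therefore firm, but the size is not. On the planned attrition it is about 74–79% of the true risk with constant hazard and 83–88% with front-loaded onset, and lower still for events confined to the second half-year. These figures rest on assumed risks and onset shapes and on drop-out independent of events.

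For the comparison of arms, what the plan supports is narrower: equal drop-out shrinks a real difference. A false or masked difference, and misleading Fisher p-values, are conditional on unequal drop-out, which the documents neither predict nor exclude.

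**What to change.** In SAP 12.2.2:

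- Keep the crude n (%).
- Add, by arm, subjects with a first event per 100 subject-years at risk (time to first event, otherwise to last contact) to the TEAE, related-TEAE, AESI and SAE tables T14.1.9.5.3–5.8 and 5.15–5.18.
- Add Kaplan-Meier cumulative incidence with 95% CIs at Week 52 for any TEAE, any related TEAE and the nasal AESI group. Add the same at the 30-week cut-off once that is settled: SAP 12.2.2 equates 30 weeks with 182 days, but 30 × 7 = 210.
- State that these estimates assume non-informative censoring, and show them beside drop-out by arm and reason.
- Base statements about 52-week incidence, and its comparison between arms, on these estimates. Label the Fisher p-values as descriptive comparisons of crude proportions.

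No new data are needed: L16.2.5.3 and L16.2.7.1 already list dose, exit and event dates. The cost is SAP wording, more output and an added censoring assumption. The change should be made before unblinding, so that it is not a post-hoc choice.

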5.5 Study Rationale

It has been suggested that olopatadine hydrochloride is clinically superior to other anti-allergy molecules because of its strong antihistamine activity and unique ocular mast cell stabilizing

properties.³ The efficacy and safety of mometasone furoate NS, 50 µg (Nasonex[®] NS 200 µg total daily dose, QD) in the prophylaxis and treatment of nasal symptoms of SAR, nasal congestion associated with SAR and the treatment of perennial allergic rhinitis (PAR) have been evaluated in 18 controlled trials, and 1 uncontrolled clinical trial, in approximately 3000 adults (aged 17 to 85 years) and adolescents (aged 12 to 16 years).¹⁰

Olopatadine hydrochloride and mometasone furoate, the monocomponents in GSP 301 NS, are approved in the US. The safety, including long-term safety, of these drugs is well established.

As the proposed GSP 301 NS is to be used to treat chronic rhinitis, it is important to evaluate the safety of the product during long-term use. The US Food and Drug Administration (FDA) guidance on the development of drug product for AR recommends that a new product should be evaluated in a long-term (52 weeks) safety study. Therefore, the optimal dose and regimen determined based on the Phase 2 study, will be further tested in this protocol to evaluate the long-term safety and efficacy of GSP 301 NS compared with placebo NS formulations.

GSP 301 NS is an aqueous nasal spray containing olopatadine hydrochloride and mometasone furoate monohydrate as the active ingredients in an aqueous solution with an approximate pH of [REDACTED]. Although, matching pH of the active product [REDACTED] is essential to maintain blinding for efficacy purposes; the low pH in the placebo treatment may impact the interpretation of the safety data because the frequencies of commonly occurring adverse events (AEs) in the GSP301 NS group may be underestimated when compared with the low pH placebo treatment group. To address this issue, an additional placebo NS with a higher pH of approximately [REDACTED] is being evaluated in this study as recommended by the US FDA. Thus, the primary objective of this study is to compare the long-term safety and tolerability of GSP 301 NS with two GSP 301 placebo NS formulations over 52 weeks of treatment in subjects (aged ≥12 years) with PAR. Additionally, the long-term efficacy of GSP 301 NS will also be evaluated.

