### 3.0 Objectives

#### 3.1 Primary Objective

- To compare the long-term safety and tolerability of GSP 301 NS with 2 GSP 301 placebo NS formulations over 52 weeks of study treatment

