### 12.3 Efficacy Analyses of Efficacy Endpoints

For all efficacy statistical analysis of efficacy endpoints, the comparison of interest will be GSP 301 NS vs. placebo NS pH [REDACTED]. The statistical analysis will only include up to week 52 data in the analysis.

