## STATISTICAL ANALYSIS PLAN

|  |                                    |                                  |
|--|------------------------------------|----------------------------------|
| Protocol Number:
GPL/CT/2014/018/III
(Study No. GSP 301-303) | SAP Version Number:
Version 1.0 | SAP Version Date:
04-Apr-2017 |
|--|------------------------------------|----------------------------------|

site-by-treatment and baseline-by-treatment will be investigated separately in the model and will only be included in final model if they are statistically significant at the  $\alpha=5\%$  level. An unstructured (UN) covariance will be assumed. If the model does not converge using the unstructured covariance structure, the autoregressive (order 1) AR(1) structure will be used. If this also does not converge other covariance structures deemed appropriate to fit the data will be used. This method will assume that any missing data is Missing at Random (MAR). The statements of a SAS PROC MIXED analysis would be (if the interactions of treatment\*baseline and treatment\*site is not statistically significant):

```
proc mixed;  
class subject treatment site week;  
model change = treatment site baseline week;  
repeated week / subject = subject type=UN;  
lsmeans treatment / cl diff e ;  
ods output lsmeans=lsmeans ;  
ods output diffs=diffs ;  
run ; quit ;
```

The adjusted means for each treatment and the estimated treatment differences for the treatment comparisons will be presented together with 95% confidence intervals for the differences and p-values for the treatment comparisons. The adjusted means and estimated treatment differences for the treatment comparisons will also be plotted, with corresponding 95% confidence intervals.

The responses for the first 6, 30 and 52 weeks of treatment will all be analysed in separate statistical models.

A multiple, imputation-based approach may be considered for handling missing data for AM rTNSS upon review of amount of missing data observed.

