| Moderate (n2(%))                                | xxx (xx.x)                                     | xxx (xx.x)                                     | xxx (xx.x)               |
| Severe (n2(%))                                  | xxx (xx.x)                                     | xxx (xx.x)                                     | xxx (xx.x)               |
| Not Related (n2(%))                             | xxx (xx.x)                                     | xxx (xx.x)                                     | xxx (xx.x)               |
| Related (n2(%))                                 | xxx (xx.x)                                     | xxx (xx.x)                                     | xxx (xx.x)               |
| Death (n2(%))                                   | xxx (xx.x)                                     | xxx (xx.x)                                     | xxx (xx.x)               |
| Serious AE (n2(%))                              | xxx (xx.x)                                     | xxx (xx.x)                                     | xxx (xx.x)               |

N1: number of subjects in safety analysis sets in treatment group; n1(%): percentage based on N1

N2: number of adverse events in treatment group; n2(%): percentage based on N2

Data source: xx

Created on: ddmmmyy hh:mm

Page 1 of N

**T14.1.9.5.2 Overall Summary of Treatment Emergent Adverse Events after 30 Weeks of Study Treatment  
(Safety Analysis Set)**

Repeat of T14.1.9.5.1 for after 30 weeks of study treatment

|  |                                    |                                  |
|--|------------------------------------|----------------------------------|
| Protocol Number:
GPL/CT/2014/018/III
(Study No. GSP 301-303) | SAP Version Number:
Version 1.0 | SAP Version Date:
04-Apr-2017 |
|--|------------------------------------|----------------------------------|

**T14.1.9.5.3 Summary of Treatment Emergent Adverse Events after 52 Weeks of Study Treatment  
(Safety Analysis Set)**

| Body System                    | MedDRA Term | GSP 301 placebo
NS pH [REDACTED]
(N=xxx) |                  | GSP 301 placebo
NS pH [REDACTED]
(N=xxx) |                  | GSP 301
NS
(N=xxx) |                  | Fisher's
P-value |
|--------------------------------|-------------|--|------------------|--|------------------|--------------------------|------------------|---------------------|

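### SAP 12.2.2 compares TEAEs only by an overall three-group Fisher p-value per row; neither contrast of GSP 301 with a placebo is named or given with its precision

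*SAP*

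**What the plan says.** The primary objective (SAP 3.1, same in Protocol 6.1) is "To compare the long-term safety and tolerability of GSP 301 NS with 2 GSP 301 placebo NS formulations over 52 weeks of study treatment". Protocol 5.5 explains why there are two placebos: the pH-matched one protects the blind, but against it the frequencies of common adverse events "in the GSP301 NS group may be underestimated when compared with the low pH placebo treatment group", so a higher-pH placebo was added.

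For adverse events, SAP 12.2.2 plans per-arm description: "Summaries of the number and percentage of subjects with TEAEs and the number of TEAEs experienced will be presented by treatment group". The one comparative output is this: "The overall p-value of the comparison among three treatment groups by SOC and PT will be produced", by Fisher's exact test, for each SOC, each PT and any TEAE. The shell headed "T14.1.9.5.3 Summary of Treatment Emergent Adverse Events after 52 Weeks of Study Treatment" follows suit, with events and n (%) per arm and a single Fisher p-value column. Shells T14.1.9.5.4 to 5.8 (30 weeks, treatment-related, AESI, treatment-related AESI) reuse it; for AESIs the instruction is "Repeat of T14.1.9.5.3 for AESI". The severity, relationship and SAE shells have no comparative column.

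The secondary objective gets more. SAP 12.3 states: "For all efficacy statistical analysis of efficacy endpoints, the comparison of interest will be GSP 301 NS vs. placebo NS" (the pH is redacted). SAP 12.3.2.1 adds that "the estimated treatment differences for the treatment comparisons will be presented together with 95% confidence intervals".

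**The concern.** Two placebos with different purposes imply two contrasts. The difference from the pH-matched placebo shows what the active ingredients add to the vehicle at that pH. The difference from the higher-pH placebo guards against an acidic vehicle hiding part of the adverse-event burden. A three-group test merges both and adds a third comparison, placebo against placebo, which is not an objective.

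What is at stake is how the primary safety comparison reads. A small overall p-value does not say which placebo GSP 301 differs from, in which direction or by how much, and it can partly reflect a gap between the placebos. A large one does not show what excess over either placebo has been ruled out, and with 100 subjects per placebo that excess may not be small.

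**Working it through.** **Inputs from the documents.** Planned arm sizes 400, 100 and 100; exposure targets of 300 subjects for 6 months and 100 for 1 year; attrition of 25% and 50% (Protocol 13.1, SAP 8.0). The documents give no TEAE rates, so all event counts below are assumed.

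**The plan's own figure.** 300/(1 - 0.25) = 400 and 100/(1 - 0.50) = 200. The 6-month target therefore gives the stated 400. Arm sizes come from exposure, not from the precision of a difference against either placebo.

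**Methods.** The overall p is the exact 2x3 Fisher test by full enumeration. The 95% CI for a risk difference is Newcombe's: with Wilson limits (l, u) for each arm and d = p1 - p2, the lower limit is d - sqrt((p1 - l1)^2 + (u2 - p2)^2) and the upper limit is d + sqrt((u1 - p1)^2 + (p2 - l2)^2).

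**Example 1: A 10/100, B 2/100, GSP 301 40/400.** If A is the low-pH placebo, this is the pattern that Protocol 5.5 is worried about. Wilson limits in percent: GSP 301 10.0 (7.43 to 13.33), A 10.0 (5.52 to 17.44), B 2.0 (0.55 to 7.00).
- Overall Fisher p = 0.017.
- GSP 301 minus A: 0.0; lower 0 - sqrt(2.57^2 + 7.44^2) = -7.9; upper 0 + sqrt(3.33^2 + 4.48^2) = 5.6.
- GSP 301 minus B: 8.0; lower 8 - sqrt(2.57^2 + 5.00^2) = 2.4; upper 8 + sqrt(3.33^2 + 1.45^2) = 11.6.
- A minus B: 8.0; lower 8 - sqrt(4.48^2 + 5.00^2) = 1.3; upper 8 + sqrt(7.44^2 + 1.45^2) = 15.6.

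The overall test is significant while GSP 301 and A have the same rate. Part of the signal is the gap between the two placebos.

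**Example 2: 7/100, 7/100, 48/400.** Wilson limits: GSP 301 12.0 (9.17 to 15.55), placebo 7.0 (3.43 to 13.75).
- Overall Fisher p = 0.19.
- GSP 301 minus either placebo: 5.0; lower 5 - sqrt(2.83^2 + 6.75^2) = -2.3; upper 5 + sqrt(3.55^2 + 3.57^2) = 10.0.

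The test is not significant, yet an excess of up to 10 points over either placebo remains compatible with the data.

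**Precision at 400 against 100, equal assumed rates**

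| Rate in both arms | Newcombe 95% CI for the difference (points) |
|---|---|
| 3% | -5.6 to 2.9 |
| 10% | -7.9 to 5.6 |
| 20% | -9.6 to 7.9 |
| 50% | -10.8 to 10.8 |

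**The case against.** The best defence is that this is mainly a matter of presentation. The AE endpoints are proportions and incidence, and these are reported by arm. SAP 6.0 states no hypotheses, so no decision depends on the p-value. Protocol 13.7.2 already planned an across-group Fisher or similar test. All of this stands, and it limits the point to estimation.

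The comparison with efficacy is also not quite like for like. A model-adjusted difference cannot be rebuilt from summary tables and so has to be specified, whereas an unadjusted risk difference can be rebuilt from n and N. SAP Appendix 1 also allows tables to be added after the analysis. These arguments stand only in part: a table added afterwards does not pre-specify the contrasts, and the primary comparison should not have to be worked out by the reader.

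A reader might infer more than the documents support:
- That the plan gives no information on precision. It gives everything needed for an interval; it does not name or show one.
- That a single test covers the whole study. There is one p-value per row.
- That the crude proportions are biased by dropout. The documents give one attrition estimate and no split by arm, so differential attrition would be speculation.

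**Conclusion.** The point holds as a gap in estimation. The primary objective is comparative and the two placebos serve different purposes, yet the only comparative TEAE statistic estimates neither difference. It is not a departure from the endpoints, and no planned result is wrong or biased. A stronger charge, that the primary safety analysis is invalid, is not supported: the per-arm results are sound and no decision rule exists.

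The size depends on event rates that the documents do not give. At assumed equal rates of 3% to 50% and the planned 400 against 100, each interval would reach about 3 to 11 points on the side of excess risk. The two worked examples rest on invented counts. They show what the overall p-value can conceal, not what this trial will find. The change is worth making because it is cheap and completes the comparison that the objective calls for.

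**What to change.** In SAP 12.2.2 and 12.2.3 and shells T14.1.9.5.3 to 5.8, add the risk difference for GSP 301 minus each placebo separately, with a 95% CI by a named score-type method (Newcombe or Miettinen-Nurminen). Restrict it to any TEAE, treatment-related TEAEs and the four AESI groups of SAP 12.2.3 (nasal, ophthalmic, somnolence, others), not each PT. State that the intervals are unadjusted and for estimation. Keep the overall Fisher p-values, labelled descriptive, and add no pairwise p-values.

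Cost: SAP wording, extra columns in six shells and a subject-level row per AESI group; no new data. The number of intervals is 2 tables x 2 placebos = 4 for any TEAE, another 4 for treatment-related TEAEs, and 2 tables x 4 groups x 2 placebos = 16 for AESIs, 24 in all. Using each of the ten listed AESI PTs instead would give 8 + 2 x 10 x 2 = 48, many of them for rare events where they would add little. The downside is slightly wider tables and intervals without multiplicity control: with no true differences, about 24 x 0.05 = 1.2 would be expected to exclude zero, which is why the estimation label matters.
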